1.0 Objectives*

Magnetic Resonance Fingerprinting (MRF) and Q-space Trajectory Imaging (QTI) are advanced new magnetic resonance imaging (MRI) sequences that provide rapid quantitative tumor metrics and enable visualization of the tumor microstructure, respectively. This would have substantial value in diagnostics and tumor characterization in cases such as insufficient biopsy specimens, MRI-guided treatment planning, and in evaluating treatment response and differentiating residual tumor from treatment related changes. Furthermore, quantitative metrics from MRF and QTI may provide prognostic or predictive biomarkers that guide the proper oncologic workup and treatment for the patient. We hypothesize that QTI provides deeper insight into the tissue microstructural environment and that quantitative metrics from QTI and MRF accurately characterize the gynecological malignancy in comparison with the tumor histology. Furthermore, we hypothesize that MRF and QTI provide prognostic information valuable to the patient and treating physician.

Primary Objective

- to investigate the feasibility of advanced MRI sequences in participants with gynecologic malignancy and in control participants with benign uterine fibroids by measures of image quality and by comparing the MRI parameters between different tumor entities and normal anatomic structures

Secondary Objectives

- to study the diagnostic value of MRF and QTI in characterizing the tumor by comparing the tumor parameters with normal structures, benign fibroids, and tumor histology
- to study the prognostic value of MRF and QTI by comparing tumor parameters with treatment effect and participant outcome

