3.0 Inclusion and Exclusion Criteria*

Patients with gynecological cancer who are referred to receive treatment at Brigham and Women's Hospital (BWH) and/or Dana-Farber Cancer Institute (DFCI), and who will undergo routine clinical standard of care pelvic MRI, are eligible to participate in the study. Subjects with benign uterine fibroids referred to routine pelvic MRI at BWH will serve as controls.

Inclusion Criteria

- Participants with suspected or histologically confirmed diagnosis of primary or recurrent gynecological cancer including uterine endometrial, cervical, vaginal, vulvar, ovarian, and smooth-muscle tumors undergoing routine clinical standard of care pelvic MRI
- Control subjects with benign fibroids undergoing routine clinical standard of care pelvic MRI
- Age \geq 18 years
- ECOG performance status of \leq 2, based on treating physician's discretion (Appendix A)
- Ability to understand and the willingness to sign a written informed consent document

Exclusion Criteria

- Contraindication to MRI identified by the MR procedure screening form, such as a pacemaker, aneurysm clip, inner ear implant, neurostimulator, or other MR non-compatible device or implant
- Uncontrolled intercurrent illness including, but not limited to ongoing or active infection, symptomatic congestive heart failure, unstable angina pectoris, cardiac

arrhythmia, or psychiatric illness/social situations that would limit compliance with study requirements

- Adults unable to consent
- Non-english speaking subjects
- Pregnant women
- Prisoners

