11.0 Data Management* and Confidentiality

11.1 Data analysis plan and statistical procedures

Primary endpoint of this study is to evaluate the feasibility of MRF and QTI in gynecological pelvic MRI. Feasibility will be assessed in two ways. First, the aspects of image quality such as artifacts, sharpness, and noise will be evaluated by two radiologists. Second, regions-of-interest (ROI) of the tumor and normal tissue (uterine normal endometrium, myometrium, cervical stroma, ovaries) will be recorded and ROI-based parameters from MRF (T1 and T2 relaxation values) and QTI (total mean kurtosis MK_T , microscopic anisotropy MK_A , isotropic heterogeneity MK_I , fractional anisotropy FA, microscopic fractional anisotropy μFA) will be compared between the tumor and normal tissue, and between different tumor histologies. One-way analysis of variance will be used to determine the statistical difference of each MRF and QTI value between the malignant tumors, benign fibroids, and normal tissue.

Secondary endpoint is to assess the predictive and prognostic value of MRF and QTI in gynecological malignancies. For this purpose, MRF and QTI parameters from gynecological malignancies will be compared with the treatment effect

assessed by clinical examination and/or cross-sectional follow-up imaging, and the participants' outcome by means of Kaplan-Meier method with log rank test, and Cox proportional-hazards model.

Variables that will be collected include the quantitative MRI parameters, demographic information (age, sex), clinical variables (diagnosis, tumor stage, histopathologic and molecular data, laboratory results, treatment, dates of diagnosis and treatments), follow-up images, and outcome data (recurrences, survival). An Excel database including MRI and clinical variables will be developed for the purposes of this study.

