11.2 Power analysis

The sample size calculation is exploratory in nature since no protocols with MRF or QTI in gynecological imaging have been published. One prior publication reports the range of traditional T2 relaxation values in one patient with endometrial cancer [15]. Based on the average value of 78 ms T2 relaxation time in endometrial cancer, and on the assumption of 5% difference to other histologies and SD of 5 ms, the calculated targeted sample size is 27 patients per group with power set at 80% and type I error rate of 5% (www.sample-size.net/sample-size-means/).

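### The accuracy hypothesis and diagnostic-value objective are analysed only by comparing group means, which does not measure how well a parameter classifies a lesion

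*Combined protocol and SAP*

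**What the plan says.** Section 1.0 hypothesizes that "quantitative metrics from QTI and MRF accurately characterize the gynecological malignancy in comparison with the tumor histology". Its first secondary objective is "to study the diagnostic value of MRF and QTI in characterizing the tumor"; the stated means is to set tumor values against those of normal anatomy and fibroids, and against the histological findings. Section 8.0 adds no endpoint definition and refers back to section 1.0.

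Section 11.1 places the tissue comparison under the primary feasibility endpoint: "One-way analysis of variance will be used to determine the statistical difference of each MRF and QTI value". The three groups in that analysis are cancers, fibroids and normal tissue. It also says that parameters will be compared between tumor histologies, but names no other method for this. For the secondary endpoint it states: "Secondary endpoint is to assess the predictive and prognostic value of MRF and QTI in gynecological malignancies", with Kaplan-Meier, log-rank and Cox methods. Diagnostic value is not named as an endpoint there.

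Section 3.0 admits "Participants with suspected or histologically confirmed diagnosis" of gynecological cancer, while the controls enter as women with benign fibroids. Section 11.2 bases the sample size on a difference in mean T2, and section 23.0 applies the resulting 27 to the malignancy and fibroid groups for each sequence.

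**The concern.** Accuracy and diagnostic value concern how well one woman's measurement assigns her lesion to the right class. An ANOVA asks whether group means differ by more than chance would explain. The two can diverge: distributions that overlap heavily still give a small p-value once the groups are large enough. The planned output contains a test of means and nothing that shows the overlap.

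The stake is in the reporting. A significant difference in means could be written up as support for the accuracy hypothesis or for diagnostic value, with no figure by which a reader could judge it. A later study would also have no estimate of discrimination, and no interval, to plan from.

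The contrast adds a limit of its own. Confirmed or suspected cancers are set against lesions already regarded as benign, which is an easier task than sorting lesions of unknown nature.

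**Working it through.** **Inputs from the documents.** Mean T2 of 78 ms, a 5% difference from other histologies, SD 5 ms, 80% power and 5% type I error (section 11.2); 27 malignant and 27 fibroid participants per sequence (section 23.0).

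**Assumptions, not in the documents.** The same difference applies to malignant versus fibroid; values are normal with equal SD; the test is two-sided; specificity is fixed at 80% or 90%.

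**1. The plan's own figure.**
- Difference = 0.05 × 78 = 3.9 ms; d = 3.9/5 = 0.78.
- Normal approximation: n = 2 × [(1.960 + 0.842)/0.78]² = 25.8, so 26 per group.
- Two-sample t-test: 26.8, so 27 per group, with power 80.3% at 27.

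The stated 27 is reproduced.

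**2. Discrimination at that effect size.**
- AUC = Φ(d/√2) = Φ(0.78/1.414) = 0.71.
- Sensitivity at 80% specificity = Φ(0.78 − 0.842) = 0.475, or 48%.
- Sensitivity at 90% specificity = Φ(0.78 − 1.282) = 0.31.
- At the midpoint cut-off, sensitivity = specificity = Φ(0.78/2) = 0.65.

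**3. Smallest observed difference that reaches p<0.05 with 27 versus 27.**
- d = t(0.975, 52 df) × √(2/27) = 0.546, or 0.546 × 5 = 2.7 ms.
- AUC = Φ(0.546/√2) = 0.65; sensitivity at 80% specificity = Φ(0.546 − 0.842) = 0.38.

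**4. Effect needed for 80% sensitivity with 80% specificity.**
- d = 2 × 0.842 = 1.68 (AUC 0.88), more than twice the planning difference.

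**5. Three-group ANOVA.** If tumor differs by 0.78 SD from two equal groups, with 27 independent values in each of the three, power is about 84%. The picture does not change.

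**6. Precision of an AUC with 27 versus 27 (Hanley-McNeil).**
- With A = 0.709: Q₁ = A/(2 − A) = 0.549, Q₂ = 2A²/(1 + A) = 0.588, A² = 0.503.
- SE² = [A(1 − A) + 26(Q₁ − A²) + 26(Q₂ − A²)]/(27 × 27) = 0.0050, so SE = 0.071.
- 95% CI = 0.709 ± 1.96 × 0.071, about 0.57 to 0.85.

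**7. Sensitivity to the SD.** With the same 3.9 ms, an SD of 7.5 ms gives d = 0.52, AUC 0.64 and power 47%; an SD of 10 ms gives d = 0.39, AUC 0.61 and power 29%.

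**The case against.** The best defence is that this is a first look. The primary endpoint is feasibility, section 15.0 calls the study a pilot, section 11.2 calls the sample-size calculation exploratory, and section 2.0 says that neither sequence has been studied in gynecological malignancy. The objective proposes to study diagnostic value by comparing parameters, and section 11.1 does compare them. An AUC from 27 versus 27 would be too imprecise to settle whether a metric is accurate. All of this stands, and it is why the remedy should be small and labelled exploratory. It does not close the gap: the hypothesis speaks of accurate characterization, and a comparison of means cannot address that at any sample size.

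The illustration has limits too. The 5% difference starts from "Based on the average value of 78 ms T2 relaxation time in endometrial cancer" and is stated against other histologies, not fibroids. It concerns T2 alone; the documents give no effect size for T1 or any QTI parameter. A planning difference is not a prediction of marker performance.

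Three stronger readings are tempting, and the documents do not support them:
- A reader might infer that the study can succeed with a marker that misses half the cancers. The protocol sets no success rule for the diagnostic objective and claims only to study diagnostic value. A miss rate near one half holds only at the assumed specificity of about 80% and the borrowed effect size; at the midpoint cut-off about 35% are missed.
- A reader might infer that picking the best of the five QTI parameters will inflate apparent accuracy. No selection of a parameter or cut-point is planned.
- A reader might infer that women enrolled as suspected need a formal accuracy analysis of their own. Their number is not given, and they form an unknown part of 27 malignancy participants per sequence spread over several tumor types. Description is as much as the data are likely to bear.

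**Conclusion.** The point holds as a mismatch between aim and analysis. An accuracy hypothesis and a diagnostic-value objective have no accuracy measure anywhere in the plan, and the only inferential method named for the tissue comparison tests means. Under the stated assumptions, a parameter that the study has about 80% power to declare significant would have an AUC of 0.71, and one that only just reached significance would show an AUC of 0.65. These figures illustrate how far a p-value can stand from classification; they do not forecast MRF or QTI performance, and they move with the assumed SD, effect and specificity. The image-quality assessment and the survival analyses are unaffected. The change is worth making because it decides what may be said about diagnostic value at the end.

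**What to change.** In section 11.1, add the following, labelled exploratory:
- For each MRF and QTI parameter, the AUC for malignant tumor versus fibroid with a 95% CI (DeLong or bootstrap), and sensitivity at a specificity stated in advance.
- An optimism correction by bootstrap, only if a best parameter or a cut-point is chosen from the data.
- A statement that this contrast uses controls already known to be benign, so the AUC does not describe performance in lesions of unknown nature.
- A descriptive summary of women enrolled as suspected, by final histology.
- A rule that any statement on accuracy or diagnostic value rests on the AUC interval, not on the ANOVA p-value.

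If the sponsor prefers not to add these, the alternative is to reword the hypothesis in section 1.0 so that it says the metrics differ between groups.

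The cost is a few lines of text and a small analysis of data that are already to be collected, with no additional participants or scans. The intervals will be wide, and the suspected group may be too small to say much.

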2.0 Background*

Uterine cervical, endometrial, and ovarian cancer are the most common gynecologic malignancies, with cervical cancer being worldwide the leading cause of cancer-related death in women. Conventional MRI is routinely used in gynecologic malignancies for its ability to depict the extent of disease at diagnosis providing guidance in staging and treatment planning [1–3]. Diffusion weighted imaging (DWI) and dynamic contrast enhanced MRI further improve tumor delineation and characterization and are often included into standard protocol [4]. Moreover, DWI has shown promise regarding histological grading and subtype differentiation within endometrial and cervical cancer, however, results are not fully consistent [2, 5].

MRF is a recently introduced approach in accelerating multiparametric quantitative MR imaging [6]. Quantitative MRI methods, as opposed to traditional visual assessment of images, provide objective parameters and would particularly be advantageous in oncology for diagnosis, treatment response assessment and follow-up to reduce subjectivity of image interpretation. Traditional quantitative MRI approaches, however, are relatively slow and provide only a single property at a time. In MRF, multiple tissue properties are acquired simultaneously by randomly varying the sequence parameters [7]. Pattern recognition is then used to compare each voxel's signal fingerprint with a dictionary of anticipated combinations of tissue properties, to identify the best match of a tissue property for that voxel. MRF enables simultaneous measurement of multiple tissue properties such as T1, T2, T2*, B0, proton density, and perfusion. MRF has mainly been employed in brain imaging [8]. Recently, the proof-of-principle for using MRF in abdominal imaging and prostate cancer, was reported [9, 10].

QTI is a framework for advanced diffusion MRI that enables imaging of the tissue microstructure on a sub-voxel level that is not possible with the traditional diffusion MRI [11, 12]. By using q-space trajectory encoding and a diffusion tensor distribution model, QTI improves the discrimination of diffusivity, shape, and orientation of diffusion microenvironments and therefore carries major potential for imaging the tumor microenvironment. The feasibility of QTI in brain MR imaging has been shown in pilot studies involving patients with schizophrenia and brain tumor [12–14]. Furthermore,

studies that investigate the role of QTI in unraveling the microstructure of both brain and prostate cancers are in progress at Brigham and Women's Hospital (BWH). Neither MRF nor QTI have previously been studied in gynecological malignancies.

3.0 Inclusion and Exclusion Criteria*

Patients with gynecological cancer who are referred to receive treatment at Brigham and Women's Hospital (BWH) and/or Dana-Farber Cancer Institute (DFCI), and who will undergo routine clinical standard of care pelvic MRI, are eligible to participate in the study. Subjects with benign uterine fibroids referred to routine pelvic MRI at BWH will serve as controls.

Inclusion Criteria

- Participants with suspected or histologically confirmed diagnosis of primary or recurrent gynecological cancer including uterine endometrial, cervical, vaginal, vulvar, ovarian, and smooth-muscle tumors undergoing routine clinical standard of care pelvic MRI
- Control subjects with benign fibroids undergoing routine clinical standard of care pelvic MRI
- Age \geq 18 years
- ECOG performance status of \leq 2, based on treating physician's discretion (Appendix A)
- Ability to understand and the willingness to sign a written informed consent document

Exclusion Criteria

- Contraindication to MRI identified by the MR procedure screening form, such as a pacemaker, aneurysm clip, inner ear implant, neurostimulator, or other MR non-compatible device or implant
- Uncontrolled intercurrent illness including, but not limited to ongoing or active infection, symptomatic congestive heart failure, unstable angina pectoris, cardiac

arrhythmia, or psychiatric illness/social situations that would limit compliance with study requirements

- Adults unable to consent
- Non-english speaking subjects
- Pregnant women
- Prisoners

4.0 Study-Wide Number of Subjects*

N/A

5.0 Study-Wide Recruitment Methods*

N/A

6.0 Multi-Site Research*

N/A

7.0 Study Timelines*

Participation in this research study requires 10–15 minutes additional scanning time to perform QTI or MRF along with the routine clinical standard of care pelvic MRI. No other procedures or extra hospital visits are required by the participants. Anticipated duration to enroll all study subjects is 1–2 years. The estimated date to complete this study (complete primary analyses) is 05/31/2021.

8.0 Study Endpoints*

Please see section 1.0 for primary and secondary study objectives.

9.0 Procedures Involved*

The eligibility of participants with gynecologic cancer will be evaluated by the treating gynecologic surgeon or oncologist during the routine standard of care practice at

The Value of Advanced MR Imaging in Gynecological Tumors and Benign Uterine Fibroids

BWH/DFCI. If a participant meets the inclusion criteria, she will be informed about the study both orally and in paper by handing out the informed consent form. If the subject is willing to participate in the study, her signature to the consent form is obtained by the treating physician at the end of the appointment. In case the participant requests time for reflection, the consent signature can be obtained just prior to MRI by the research coordinator.

The eligibility of control participants with benign fibroid(s) is evaluated by the treating interventional radiologist based on the referral and a phone call made to the participant to give information about the study (Phone Script in Appendix B). Upon eligibility, informed consent will be sent by email or mail. Signature to the consent form will be obtained by a research coordinator prior to the MRI scan.

If the subject is willing to participate in the study, the advanced MRI sequence (either QTI or MRF) will be run along with the routine standard of care MRI. If the subject wishes not to participate, only standard of care MRI sequences will be performed according to the routine protocol.

Institutions will register eligible participants in the Clinical Trials Management System (CTMS) OnCore as required by DF/HCC SOP REGIST-101. When required by REGIST-101, registration must occur prior to the initiation of protocol-specific procedures or assessments.

Routine clinical standard of care pelvic MRI will be performed using a clinical 3T MRI scanner at BWH. The advanced MRI sequence (MRF or QTI) will be supplementary and included along with the current clinical exam. No invasive procedures are needed for MRF or QTI. No extra hospital visit is required related to this study. The duration of routine clinical pelvic MR exam is approximately 30–45 minutes. Running MRF or QTI along with the routine clinical protocol will add this scanning time by approximately 10–15 minutes. There are no reported toxicities related to MRI itself when all the safety guidelines are being followed. No intravenous contrast agent is needed for the advanced MR

sequences (QTI and MRF). Scanning time will be increased with 10–15 minutes which may cause discomfort to participants due to laying on the scanning table for a longer period of time.

Follow-up data including treatment outcome, tumor histology, clinical variables, laboratory results, medical images, and survival data, will be collected from the participant's electronic medical records. For survival data, the duration of follow-up is up to 4 years after participation and the MRI scan with new MRI methods.

10.0 Data and Specimen Banking*

N/A

11.0 Data Management* and Confidentiality

11.1 Data analysis plan and statistical procedures

Primary endpoint of this study is to evaluate the feasibility of MRF and QTI in gynecological pelvic MRI. Feasibility will be assessed in two ways. First, the aspects of image quality such as artifacts, sharpness, and noise will be evaluated by two radiologists. Second, regions-of-interest (ROI) of the tumor and normal tissue (uterine normal endometrium, myometrium, cervical stroma, ovaries) will be recorded and ROI-based parameters from MRF (T1 and T2 relaxation values) and QTI (total mean kurtosis MK_T , microscopic anisotropy MK_A , isotropic heterogeneity MK_I , fractional anisotropy FA, microscopic fractional anisotropy μFA) will be compared between the tumor and normal tissue, and between different tumor histologies. One-way analysis of variance will be used to determine the statistical difference of each MRF and QTI value between the malignant tumors, benign fibroids, and normal tissue.

Secondary endpoint is to assess the predictive and prognostic value of MRF and QTI in gynecological malignancies. For this purpose, MRF and QTI parameters from gynecological malignancies will be compared with the treatment effect

assessed by clinical examination and/or cross-sectional follow-up imaging, and the participants' outcome by means of Kaplan-Meier method with log rank test, and Cox proportional-hazards model.

Variables that will be collected include the quantitative MRI parameters, demographic information (age, sex), clinical variables (diagnosis, tumor stage, histopathologic and molecular data, laboratory results, treatment, dates of diagnosis and treatments), follow-up images, and outcome data (recurrences, survival). An Excel database including MRI and clinical variables will be developed for the purposes of this study.

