23.0 Local Number of Subjects

Based on sample size calculation (see Section 11.2 Power Analysis), following number of participants will be included in this research study:

1. MRF for participants with gynecologic malignancy; n=27
2. MRF for participants with benign uterine fibroid; n=27
3. QTI for participants with gynecologic malignancy; n=27
4. QTI for participants with benign uterine fibroid; n=27

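### The one-way ANOVA assumes independent ROIs, but normal-tissue ROIs must come from women who also supply a lesion; its 5% level is generally not kept, in a direction the plan leaves open

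*Combined protocol and SAP*

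**What the plan says.** Section 11.1 sets out the ROI part of the feasibility assessment: "regions-of-interest (ROI) of the tumor and normal tissue (uterine normal endometrium, myometrium, cervical stroma, ovaries) will be recorded". The MRF and QTI parameters are then compared by one test: "One-way analysis of variance will be used to determine the statistical difference". Its three groups appear in the same sentence: the "difference of each MRF and QTI value between the malignant tumors, benign fibroids, and normal tissue". No paired, repeated-measures or mixed model is named.

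The comparison belongs to the primary objective. Section 1.0 assesses feasibility partly "by comparing the MRI parameters between different tumor entities and normal anatomic structures".

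There is no healthy-volunteer group. Section 3.0 states: "Subjects with benign uterine fibroids referred to routine pelvic MRI at BWH will serve as controls". Section 23.0 lists four groups of 27: malignancy and fibroid for each sequence, for example "MRF for participants with benign uterine fibroid; n=27". Under Section 9.0 each woman has one sequence: "the advanced MRI sequence (either QTI or MRF) will be run along with the routine standard of care MRI". Each ANOVA therefore draws on 27 + 27 = 54 women.

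**The concern.** Every normal ROI must come from a woman with a malignancy or a fibroid, who would normally supply a lesion ROI to the same analysis. Four normal tissues are listed, so one woman may also supply several normal ROIs. ROIs from one woman share her age, hormonal state, scanner and session, so some correlation is to be expected. A one-way ANOVA ignores it.

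At stake are the p-values and intervals for lesion against normal tissue. Three things decide whether they are too cautious or too lenient:
- which women supply the normal ROIs;
- whether the four tissues form one pooled group;
- whether normal ROIs correlate with each other more than with the lesion.

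The plan settles none of these in advance.

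**Working it through.** **Inputs from the documents.** 27 malignant and 27 fibroid women per sequence (Section 23.0); mean T2 of 78 ms, 5% difference, SD 5 ms, 80% power, 5% type I error (Section 11.2).

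**Assumptions, because the documents give no figure.** Lesion-normal correlation *a*; normal-normal correlation *b*; *k* normal ROIs per supplying woman, entered as separate observations; one lesion ROI per woman; fibroid ROIs from the control women only; equal variances; equal tissue means unless stated.

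**The plan's own figure.** 5% of 78 ms = 3.9 ms, and 3.9/5 = 0.78 SD. The normal approximation gives n = 2(1.960 + 0.842)²/0.78² = 25.8. The two-sided t-based solution is 26.8, so 27 per group, with power 80.3%. The stated 27 is reproduced. It is a calculation for two independent groups and does not cover a within-woman comparison.

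**True variance over the variance the ANOVA assumes, V:**
- All 54 women supply normals, either lesion group vs normal: V = [2 + 1/k + (1 − 1/k)b − 2a] / (2 + 1/k)
- One group supplies, its own lesions vs normal: V = [1 + 1/k + (1 − 1/k)b − 2a] / (1 + 1/k)
- One group supplies, the other group's lesions vs normal: V = [1 + 1/k + (1 − 1/k)b] / (1 + 1/k)

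The true level of a nominal 5% contrast is about 2Φ(−1.96/√V). In the first two cases the contrast is too lenient when (1 − 1/k)b > 2a. At k = 4 that means *a* below 3/8 of *b*. At k = 1 it cannot happen with positive *a*.

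| Case | Correlations | V | Formula level | Simulated level |
|---|---|---|---|---|
| All 54, k=1, malignant vs normal | a = 0.3/0.5/0.7 | 0.80/0.67/0.53 | 2.8/1.6/0.7% | about 2.9/1.5-1.8/0.6-0.8% |
| All 54, k=4 pooled, malignant vs normal | a = b = 0.3/0.5/0.7 | 0.83/0.72/0.61 | 3.2/2.1/1.2% | 3.2/2.2/1.3% |
| All 54, k=4 pooled, malignant vs normal | a = 0, b = 0.5 | 1.17 | 7.0% | 7.0-7.3% |
| All 54, k=4 pooled, malignant vs normal | a = 0.1, b = 0.5 | 1.08 | 5.9% | 6.0% |
| Malignant women only, k=4 pooled, malignant vs normal | a = b = 0.3/0.5/0.7 | 0.70/0.50/0.30 | 1.9/0.6/0.0% | 2.0/0.6-0.7/0.1% |
| Malignant women only, k=4 pooled, fibroid vs normal | a = b = 0.3/0.5/0.7 | 1.18/1.30/1.42 | 7.1/8.6/10.0% | about 7-11% across the range |
| Malignant women only, k=1, fibroid vs normal | any | 1.00 | 5% | about 5% |

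If only fibroid women supply the normals, the two lesion contrasts swap.

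**Global F test.**
- All 54 women, k = 1: 3.1% to 1.8% as the correlation goes from 0.3 to 0.7.
- Malignant women only, k = 4 pooled, one common correlation: 4.6% to 5.7%.
- All 54 women, k = 4 pooled, b = 0.5: 7.5-7.7% at a = 0 and 6.2-6.4% at a = 0.1.

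**Where little happens.** At a common correlation of 0.1 the contrasts run at 3.8-5.9%. Malignant vs fibroid compares different women and stays at about 5% when the tissue means are equal.

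**Power for malignant vs normal, k = 1, correlation 0.3/0.5/0.7.**
- All 54 supply, 0.78 SD: ANOVA contrast 92.9/94.6/96.2%, paired test in the 27 malignant women 90.9/97.4/99.9%.
- All 54 supply, 0.5 SD: 56.4/57.4/57.9% against 56.3/71.2/89.8%.
- Only malignant women supply, 0.78 SD: 84.6/88.8/93.8% against 90.9/97.4/99.9%.

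**A separate effect: pooling unlike tissues.** This needs no correlation. With four pooled ROIs from all 54 women there are 216 normal ROIs and 270 − 3 = 267 residual df. If the tissue means have SD 5 ms, the residual variance is about 25 + (216/267) × 25 = 45.2 instead of 25. For malignant vs fibroid the rejection limit becomes about 1.97 × √(45.2 × 2/27) = 3.6 ms, while the true standard error is √(50/27) = 1.36 ms. Power at 3.9 ms is Φ((3.9 − 3.6)/1.36), about 59%, against about 82% without the spread. A spread of 2.5 ms gives 76%. These spreads are assumptions.

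**Candidate replacements.** Paired differences hold 4.7-5.3% in the cases examined. A mixed model with tissue as a fixed factor and only a random intercept for woman holds about 5% under one common correlation. With a = 0 to 0.1 and b = 0.5, it gives 9-10% for malignant vs a named tissue and 10-11% for malignant vs fibroid.

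**The case against.** The strongest reply is that Section 11.1 names an ANOVA and no pairwise contrasts. Its global F stays between about 2% and 6% under one common correlation. The figures of 7% and above need several normal ROIs per woman entered as separate observations. They also need either supply from one group only or a lesion-normal correlation well below the normal-normal one. Section 11.1 does not limit normal ROIs to one group, and it lists the tissues by name, so pooling is only one reading. The correlations are assumed. The study is a pilot, Section 11.2 calls its sample size exploratory, and no decision rests on the ANOVA.

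Most of this stands, and it limits the harm. It does not restore independence, because the enrolment provides no separate source of normal tissue. The reply also depends on choices that the plan has not made.

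A reader might infer more than the documents support:
- *The ANOVA inflates false positives.* Not in general. With one normal ROI per woman, the comparison within the same women is too cautious.
- *It is always cautious if both groups supply normals.* That requires *a* not to fall far below *b* when several ROIs are pooled.
- *Every comparison is invalid.* The pairing does not affect malignant vs fibroid. Cross-group contrasts with one ROI per woman are about nominal.
- *The 27 per group is wrong.* It follows from its own inputs.
- *A random intercept settles the matter.* Under unequal correlations it can do worse than the ANOVA, including for malignant vs fibroid.

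**Conclusion.** The concern holds in a limited form. The independence assumption of the planned test fails for lesion against normal tissue, as inferred from the enrolment. The nominal 5% level is generally not kept where a lesion and a normal ROI from the same women are compared, or where several normal ROIs per woman are pooled. The error can go either way: from below 1% to about 11% for single contrasts, and from about 2% to 8% for the global F, within the correlations tried (0.3 to 0.7, and a = 0 to 0.1 with b = 0.5).

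The consequence is modest. At the planned 0.78 SD little power is lost if all women supply normal ROIs. More is lost for a smaller shift with correlation of 0.5 or higher, or if only malignant women supply them. The loss of power from pooling unlike tissues is a separate matter and depends on an assumed spread of tissue means. The plan should be corrected before analysis because the change is cheap and the comparison is part of the primary objective.

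**What to change.** For each MRF and QTI parameter, replace the single ANOVA in Section 11.1 with two analyses:

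1. Paired within-woman comparisons of the lesion minus a named normal tissue in the same woman. Keep endometrium, myometrium, cervical stroma and ovary separate, not pooled.
2. A between-women comparison of malignant and fibroid lesions, using the lesion ROIs only.

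State which women supply which normal ROIs, and that each woman contributes one value per tissue.

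If one joint model is preferred, use a mixed model with tissue as a fixed factor and either an unstructured within-woman covariance or standard errors clustered by woman. A random intercept alone is not enough.

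The cost is analysis wording and a little more analysis work, with no new patients, scans or data. The paired test drops women who lack the named tissue ROI. Where all women supply normal ROIs, it gains no power over the ANOVA at correlations of about 0.3 or less.
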